4.1 Rationale for study design

We aim to enroll patients with severe COVID-19 pneumonia and hyper-inflammation to identify the subgroup of patients for whom immunosuppression could prevent worsening of pulmonary status, including the need for ventilatory support, with the aim ultimately to improve mortality.

4.1.1 Rationale for choice of background therapy

Accumulating evidence suggests that a subgroup of patients with severe COVID-19 might have a cytokine storm syndrome. The identification and treatment of hyper-inflammation using existing therapies with understood safety profiles that are either in clinical development or approved in other indications is a relevant option to address the immediate need to reduce the rising mortality.

Mavrilimumab is an anti-GM CSF-R α monoclonal antibody (human isoform IgG4) previously developed by MedImmune and now in development by Kiniksa Pharmaceuticals that has been shown to inhibit the GM-CSF signaling axis in humans and improve clinical outcomes measures in a Phase 2 program in Rheumatoid Arthritis.

4.2 Rationale for dose/regimen and duration of treatment

Preliminary, publicly available data suggest efficacy of mavrilimumab at a dose of 6 mg/kg IV. However, these results are from an open-label study, and the results from our Phase II randomized, placebo controlled trial may inform the design and dose for larger studies.

In a Phase 1 single-ascending-dose (SAD) study, the pharmacokinetics (PK) of mavrilimumab were tested at doses of 0.01-10 mg/kg in patients with mild-to-moderate RA. Mavrilimumab was well-tolerated in a single IV injection up to 10 mg/kg in subjects with mild to moderate RA at all dose levels. Pharmacokinetic and pharmacodynamic simulations from studies in subjects with RA, coupled with the PK data from the Phase 1 study, indicate that a single dose of ≥ 3 mg/kg will provide EC90 (the concentration that leads to 90% maximal response) for the RA endpoint ACR50 (American College of Rheumatology 50% response criteria; data on file) for up to 22 days. Therefore, at doses ≥ 3 mg/kg, the pharmacologic profiles indicated sustained peripheral inhibition of the GM-CSF-R α signaling axis for at least three weeks.

In preclinical studies, the potential systemic effects of mavrilimumab (CAM-3001) have been investigated in a 4-week and an 11-week repeat dose cynomolgus monkey study. There were no effects attributable to intravenous (IV) administration of CAM-3001 (mavrilimumab) in doses up to 100 mg/kg/week for 4 weeks in a study conducted in accordance with Good Laboratory Practice (GLP). In an 11-week exploratory (non-GLP) study, there were no effects attributable to IV administration of CAM-3001 (mavrilimumab) following 10 mg/kg/week, and the no observed adverse event level (NOAEL) was 100 mg/kg/week. An immunocytochemistry screen to test in vitro binding of CAM-3001 (mavrilimumab) to a panel of normal human tissues revealed no non-specific or unanticipated binding of the antibody. Reference for further details on safety studies in animals and humans is made to the investigator brochure.

However, with regards to mitigation of the aberrant immune response in the setting of COVID-19, it is unclear whether blockade of GM-CSF in the lung is required in addition to abolition of signaling in the periphery. Studies with the mavrilimumab surrogate anti-mouse GM-CSF-R α antagonistic antibody, CAM-3003, were performed to interrogate the pulmonary vs peripheral pharmacodynamics of ascending single and repeat doses. Single doses of 3-30 mg/kg delivered intra-peritoneally showed no pharmacodynamic effects in the lungs (as assessed by bronchoalveolar lavage (BAL) fluid assay), despite the 3 mg/kg dose demonstrating complete receptor occupancy (RO) in the periphery. Pharmacodynamic effects in the lungs, measured by IL-6 induction from BAL cells ($72\% \pm 11\%$ inhibition), were seen following only repeated daily doses of 30mg/kg. In contrast, daily administration of 3 mg/kg did not affect IL-6 induction of BAL cells. This indicates repeated, very high doses (≥ 10 x required to completely block the signaling axis in the periphery) are required for the anti-GM-CSF-R α antibody to have an inhibitory effect on alveolar macrophages. Interestingly, Campbell et al also indicate that significant pharmacodynamic effects of the antibody on the lung cells could be observed after 5 daily doses of 30mg/kg CAM-3003 ($53\% \pm 23\%$ inhibition). The authors also indicate that PK studies using BAL measurements to quantify partitioning in the lung lumen underestimate the partitioning due to dilution with the lavage fluid.

Of further note, these studies were done in mice without underlying lung pathology, and the translatability of these studies in normal mice to humans with COVID-19 pneumonia is unclear. Nevertheless, these data suggest that a dose higher than that needed to achieve 100% RO in circulation may be required in order to achieve therapeutic concentrations in the lung. In current COVID-19 patients, it is likely that the inflammatory process afflicting the lung of severe

pneumonia patients with hyper-inflammation may lead to a higher ratio of penetration than observed in animal studies, thus allowing for potentially direct inhibitory effects on macrophages which have already migrated in the lungs.

Taken together, a dose of up to 10 mg/kg (the highest tested in humans) may be required to confer significant pharmacodynamic effects in the lung to inhibit cytokine storm and prevent further lung damage. Supported by the safety data provided by the Phase 1 study, it would be reasonable to administer a single dose of mavrilimumab at levels up to 10 mg/kg in an attempt to provide desired pharmacodynamics in COVID-19 patients, where direct inhibition of GM-CSF in the lung may be a requirement. Hypothetically, a dose of 3 mg/kg may be sufficient and reasonable to be tested, but only if higher proposed dosages in the study are found not to be safe (very close safety monitoring is proposed). Given the lethality of pulmonary complications from COVID-19, the Sponsor/Investigator, with input from COVID-19 treating physicians, is proposing that, in Phase 2, higher doses (higher than 3 mg/kg, given that this dose is apparently sufficient to completely block the signaling axis only in the periphery) be tested first. The IV route of administration is supported by Phase 1 (Burmeister 2011) safety of SAD study in RA patients. As a precaution, the IV infusion of mavrilimumab in the COVID-19 Phase 2 study will be administered at slower rates than those applied in the SAD study.

4.3 Risks and benefits

To date, there are no adverse events with a recognized causal relationship to exposure to mavrilimumab. However, there are a number of hypothetical risks that can be extrapolated from the mechanism of action. In particular, GM-CSF antagonism may interfere with immune response to infections. It is unknown how likely these effects are to occur, but their frequency may be lower with a one-time dose as compared to a longer duration to treat a chronic disease.

Frequent side effects:

- Nausea (approximately 1 in 10 subjects, self-limiting)
- Nasopharyngitis (approximately 1 in 10 subjects, self-limiting)
- Headache (approximately 1 in 10 subjects, self-limiting)

Rare but potentially life-threatening adverse reaction:

- Severe hypersensitivity reactions: While these have not been reported with Mavrilimumab, such reactions (including anaphylaxis, anaphylactoid reactions, cytokine release, and endotoxemia) have been observed after administration of other monoclonal antibodies. These reactions may be severe and may result in death.
- Leukopenia resulting in an increased risk of opportunistic infections. Mavrilimumab reduces the number of neutrophils. In some patients the reduction may be such to expose to additional (opportunistic) infection.

Additional potential side effects (of unknown frequency):

- Pulmonary alveolar proteinosis (PAP): studies have linked blockage of GM-CSF, the target of Mavrilimumab, with PAP. While the use of Mavrilimumab has not been

associated with the development of PAP in patients, a potential risk for this complication with Mavrilimumab use may exist.

- While the use of Mavrilimumab has not been associated with the development of cancer, drugs that modulate the immune response may increase the risk of cancer.
- Impaired response to vaccines. Drugs that reduce the immune response, like Mavrilimumab can impair the immune response to vaccine.
- Antibodies that inactivate the study drug thus losing its efficacy

In general, the risk to subjects in this trial may be minimized by compliance with the eligibility criteria and study procedures, close clinical monitoring, as well as periodic review of all safety data by an independent data monitoring committee (DMC).

Women of child bearing potential must be informed that taking the study treatment may involve unknown risks to the fetus if pregnancy were to occur during the study, and agree that in order to participate in the study they must adhere to the contraception requirements outlined in the exclusion criteria. If there is any question that the subject will not reliably comply, they should not be entered or continue in the study.

The benefit a patient might have by participating in the study is the close monitoring of their condition and optimization of treatment of known risk factors during the full duration of the study.

There may be unknown or unforeseen risks associated with study participation.

5 Population

The study will enroll patients identified by regular review of hospitalized COVID-19 patients to evaluate for inclusion and exclusion criteria. The study population includes patients who meet criteria of impending mechanical ventilation. Specifically, these patients will have severe pneumonia, defined as hospitalization due to COVID-19 with abnormal chest imaging, hyper-inflammation and SpO₂ <92% on room air or requirement for supplemental oxygen.

5.1 Inclusion criteria

The eligibility criteria, including the inclusion and exclusion criteria, will be verified both by a study investigator and a research nurse using checklists.

Subjects eligible for inclusion in this study must meet **all** of the following criteria:

1. Written informed consent must be obtained before any assessment is performed
2. Documented COVID19 pneumonia defined as positive SARS-CoV2 test **AND** abnormalities/ infiltrates on chest x-ray or computed tomography **AND** active fever or documented fever within 24-48 hours or ongoing anti-pyretic use to suppress fever
3. Hypoxia (Room air SpO₂ <92% or requirement for supplemental oxygen)
4. Increased serum inflammatory marker (CRP > 5 mg/dL)
5. Severity of disease warrants inpatient hospitalization

5.2 Exclusion criteria

Subjects meeting any of the following criteria are not eligible for inclusion in this study:

1. Onset of COVID-19 symptoms >14 days
2. Age < 18 years-old
3. Hospitalized >7 days
4. Mechanically ventilated
5. Serious concomitant illness which in the opinion of the investigator precludes the patient from enrolling in the trial, including (but not limited to):
 - History of immunodeficiency (congenital or acquired)
 - Neutropenia (absolute neutrophil count <1,500/mm³)
 - History of solid-organ or bone marrow transplant
 - History of current systemic autoimmune or autoinflammatory disease(s) requiring systemic immune-modulating drugs
 - History of myeloproliferative disorder or active malignancy receiving cytotoxic chemotherapy
 - Pre-existing severe pulmonary disease (i.e. steroid dependent asthma, COPD on home oxygen, or other restrictive/obstructive lung disease requiring home oxygen)
 - Pre-existing severe left ventricular systolic dysfunction (i.e. LVEF <35%)
 - Known or suspected active tuberculosis (TB), latent TB, or history of incompletely treated TB or at high risk for latent TB (from exposure or prior incarceration)
 - History of active or latent viral hepatitis (i.e. Hepatitis B or C)
 - Concomitant uncontrolled systemic bacterial or fungal infection
 - Concomitant viral infection other than COVID-19 (e.g. Influenza, other respiratory viruses)
 - History of chronic liver disease with portal hypertension
 - History of end-stage renal disease on chronic renal replacement therapy
6. Recent treatment with cell-depleting biological therapies (e.g., anti-CD20) within 12 months, cell-depleting biological therapies (such as anti-tumor necrosis factor [TNF], anakinra, anti-Interleukin [IL]-6 receptor [e.g. tocilizumab], or abatacept) within 8 weeks (or 5 half-lives, whichever is longer), treatment with alkylating agents within 12 weeks, treatment with cyclosporine A, azathioprine, cyclophosphamide, or mycophenolate mofetil (MMF) within 4 weeks
7. Recent treatment with intramuscular live (attenuated) vaccine within 4 weeks
8. Chronic or recent corticosteroid use > 10 mg/day
9. Pregnant and breast-feeding women
10. Enrolled in another investigational study using immunosuppressive therapy
11. Known hypersensitivity to mavrilimumab or any of its excipients

12. In the opinion of the investigator, unable to comply with the requirements to participate in the study
13. Women of child-bearing potential, defined as all women physiologically capable of becoming pregnant, unless they are using highly effective methods of contraception during dosing of investigational drug. Such methods include:
 - Total abstinence (when this is in line with the preferred and usual lifestyle of the subject). Periodic abstinence (e.g., calendar, ovulation, symptothermal, post-ovulation methods) and withdrawal are not acceptable methods of contraception
 - Female sterilization (have had surgical bilateral oophorectomy with or without hysterectomy), total hysterectomy, or bilateral tubal ligation at least six weeks before taking study treatment. In case of oophorectomy alone, only when the reproductive status of the woman has been confirmed by follow up hormone level assessment
 - If male and sexually active, must have documented vasectomy or must practice birth control and not donate sperm during the study and for 3 months after study drug administration.
 - Use of oral, (estrogen and progesterone), injected or implanted hormonal methods of contraception or placement of an intrauterine device (IUD) or intrauterine system (IUS), or other forms of hormonal contraception that have comparable efficacy (failure rate <1%), for example hormone vaginal ring or transdermal hormone contraception

In case of use of oral contraception women should have been stable on the same pill for a minimum of 3 months before taking study treatment.

Women are considered post-menopausal and not of child bearing potential if they have had 12 months of natural (spontaneous) amenorrhea with an appropriate clinical profile (e.g. age appropriate history of vasomotor symptoms) or have had surgical bilateral oophorectomy (with or without hysterectomy), total hysterectomy or tubal ligation at least six weeks ago. In the case of oophorectomy alone, only when the reproductive status of the woman has been confirmed by follow up hormone level assessment is she considered not of child bearing potential.

If local regulations deviate from the contraception methods listed above to prevent pregnancy, local regulations apply and will be described in the ICF.

6 Treatment

A total of 60 patients will be enrolled across all sites: 30 subjects will receive mavrilimumab 6 mg/kg IV, and 30 subjects will receive placebo infusion. No patient will receive more than one dose. Additional patients may be enrolled upon agreement of the investigators depending on speed of enrollment and availability of study drug.

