- Reduction in CRP at day 7 and day 14 (understanding that labs may be obtained until patient discharge)
- Time to negative SARS-CoV2 RNA levels in oropharyngeal or nasopharyngeal swabs
- Worst value for PaO₂/FiO₂ (or SaO₂/FiO₂ if PaO₂ not available) at day 3, day 5, day 7, day 14, day 21 and day 28, or until discharge
- Safety including number of adverse events and serious adverse events

3 Study design

This prospective, proof-of-concept Phase 2, multi-center, blinded randomized placebo-controlled study is designed to demonstrate that early treatment with mavrilimumab prevents progression of respiratory failure in patients with severe COVID-19 pneumonia and clinical and biological features of hyper-inflammation while gathering data to support a larger Phase III randomized controlled trial.

The study population includes patients who meet criteria of impending mechanical ventilation.

Enrollment: The study will be performed in approximately 4 months total, starting from the first patient enrolled with enrollment expected to complete within 2 months.

Follow-up period: The follow-up period is 60 days for each patient enrolled.

A total of 60 patients will be randomized using a 1:1 allocation ratio: 30 subjects will receive mavrilimumab at 6mg/kg IV, and 30 subjects will receive placebo infusion. The investigator, clinical team, and subject will be blinded to treatment assignment.

Participants will be identified by regular review of hospitalized COVID19 patients to evaluate for inclusion and exclusion criteria. Participants will then be approached in the standard manner by study investigator and coordinator/research nurse.

Research interventions will take place in the hospital in accordance with privacy standards.

The study team is informed on all study procedures and requirements with daily meetings and the opportunity to continuously update through secure channels.

In this multicenter consortium, each participating site will have their own IND for patients enrolled at their site. However, data collection, data analysis, and randomization scheme will be performed at one site, Cleveland Clinic C5 Research.

4 Rationale

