6.4.1 Handling of study treatment

6.4.1.1 Handling of study treatment

Study treatment must be received by a designated person at the study site, handled and stored safely and properly and kept in a secured location to which only the investigator and designated site personnel have access. Upon receipt, all study treatment must be stored according to the instructions specified on the labels and in the pharmacy manual. Clinical supplies are to be dispensed only in accordance with the protocol. Technical complaints are to be reported to the respective Kiniksa CPO Quality Assurance.

The investigator must maintain an accurate record of the shipment and dispensing of study treatment in a drug accountability log.

At the conclusion of the study, and as appropriate during the course of the study, the investigator will return all unused study treatment, packaging, drug labels, and a copy of the completed drug accountability log to the Kiniksa address provided in the investigator folder at each site.

7 Informed consent procedures

Eligible subjects may only be included in the study after providing (witnessed, where required by law or regulation), IRB -approved informed consent via site-approved procedures.

If applicable, in cases where the subject's representative(s) gives consent (if allowed according to local requirements), the subject must be informed about the study to the extent possible given his/her understanding. If the subject is capable of doing so, he/she must indicate agreement by personally signing and dating the written informed consent document.

Informed consent must be obtained before conducting any study-specific procedures (e.g. all of the procedures described in the protocol). The process of obtaining informed consent must be documented in the subject source documents.

Women of child bearing potential must be informed that taking the study treatment may involve unknown risks to the fetus if pregnancy were to occur during the study and agree that in order to participate in the study they must adhere to the contraception requirements.

A copy of the approved version of all consent forms will be kept by the Sponsor/Investigator.

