7.2.2 Pregnancy assessments

All pre-menopausal women who are not surgically sterile will have a urine or serum pregnancy test performed at the screening visit, at the investigator's discretion. Pregnancy testing is not required for post-menopausal women.

8 Study discontinuation and completion

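### Exclusion criterion 13 asks women for contraception only while a single infusion is being given, and sets no period afterwards

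*Combined protocol and SAP*

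**What the plan says.** Section 5.2, criterion 13, excludes women of child-bearing potential "unless they are using highly effective methods of contraception during dosing of investigational drug", and then lists acceptable methods. Section 6 fixes the number of doses: "No patient will receive more than one dose". Table 7-1 has a single administration mark, at Day 0.

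Other parts of the protocol bear on how long the requirement should last:

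- **Section 4.3** warns women of unknown fetal risk from a pregnancy during the study and says that, to take part, "they must adhere to the contraception requirements outlined in the exclusion criteria".
- **Section 7** repeats the warning at consent ("unknown risks to the fetus if pregnancy were to occur during the study and agree that in order to participate") and adds no duration.
- **Section 3** gives the length of the study for each patient: "The follow-up period is 60 days for each patient enrolled".
- **Section 4.2** expects a dose of 3 mg/kg or more to inhibit the peripheral "signaling axis for at least three weeks". The trial dose is 6 mg/kg.
- **The male sentence within criterion 13** says that a sexually active man without a vasectomy "must practice birth control and not donate sperm during the study and for 3 months after study drug administration".
- **Section 7.2.2** says that pre-menopausal women who are not surgically sterile "will have a urine or serum pregnancy test performed at the screening visit".

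**The concern.** With one infusion per patient, a requirement limited to dosing lasts for that infusion. Section 4.3 states the risk over a longer period, but for the requirement itself it sends the reader back to the exclusion criteria. The text that governs the duty is therefore the one with the shortest window.

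This matters because section 5.1 has an investigator and a research nurse verify eligibility from checklists. A checklist that follows criterion 13 would confirm contraception for the infusion and give the woman no date until which to continue. No later step makes up for this. Table 7-1 schedules the pregnancy test only at screening, and section 9.1.4 deals with reporting a pregnancy once it has occurred. Section 4.3 also says that a woman whose compliance is in doubt should not stay in the study. A site cannot apply that after Day 0 without knowing how long compliance is required.

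**Working it through.** The plan gives no figure to reproduce. The check compares the protocol's own periods, all counted in days from the Day 0 infusion.

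**Inputs**

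1. Women, stated period after the infusion (criterion 13): none, so 0 days read literally.
2. Study period per patient (section 3): 60 days.
3. Men (criterion 13): during the study and for 3 months after administration. Three calendar months are 89 to 92 days depending on the start date. Both parts run from about Day 0, so the window is max(60, 89 to 92) = 89 to 92 days. The two parts overlap and are not added.
4. Drug effect after one dose of 3 mg/kg or more (section 4.2): EC90 for an arthritis endpoint for up to 22 days by simulation, and peripheral inhibition for at least three weeks (21 days).

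**Differences from the literal female window**

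- Against the study period: 60 − 0 = 60 days.
- Against the male rule: 89 − 0 = 89 to 92 − 0 = 92 days, or about 90 days.
- Against the expected drug effect: at least 21 − 0 = 21 days.

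The section 4.2 figures describe efficacy exposure and peripheral pharmacology. They are not a measure of fetal exposure. They show only that, by the protocol's own account, the drug acts well beyond the infusion.

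**Is a post-dose period for women given elsewhere?** No. Sections 4.3 and 7 refer to the requirement without a duration. The 3 months mentioned for oral contraceptives in criterion 13 is a period of stable use before treatment. The local-regulations clause at the end of the criterion concerns methods of contraception, not how long they must be used.

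**The case against.** The strongest reply is that nobody would read the criterion as freeing women on Day 0. Section 4.3 frames the risk over the study and speaks of women continuing in it. The listed methods are mostly ongoing states, such as sterilization, an intrauterine device, an implant or a pill already taken for 3 months, and pregnancies are reportable at any time after consent. On this view the intent is contraception throughout the study and the fault is loose drafting. The reading of intent is reasonable. It also supports correcting criterion 13, because section 4.3 relies on that criterion for the requirement.

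A second reply is that patients learn how long to continue from the consent form, which was not available, and that the checklist has not been seen either. This stands as a limit: the gap is shown in the protocol, not in what patients were told.

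A third is that the consequence is small. Durable methods continue regardless, section 9.1.4 reports nothing suggesting a risk to fetal development, half of the 60 planned patients receive placebo, and only women on a method they can stop after discharge (pill, ring, patch, abstinence) are concerned. This also stands and limits the weight of the point. Against it, sections 4.3 and 7 still call the fetal risk unknown, and the rule for men shows that a precautionary period was thought appropriate.

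Finally, the 60-day and 3-month periods are not declared standards for women, and no half-life or washout in the documents supports 3 months specifically. That is correct. They are the protocol's own reference periods, and the only mismatch with a warning addressed to women is with the 60-day study.

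**Conclusion.** The concern holds. Followed as written, criterion 13 sets a contraception window for women that ends with the Day 0 infusion. That is 60 days short of the study period over which the protocol warns of fetal risk, and about 90 days short of what the same criterion asks of men. The protocol gives no reason for the difference.

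The conclusion rests on the literal reading of the criterion and on section 4.3 deferring to it. The number of women affected cannot be estimated from the documents, and no harm has been demonstrated. The consent form may already state a period. If so, the protocol should match it. This is a participant-safety inconsistency that should be corrected. It has no bearing on the endpoints, power or analysis.

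**What to change.** In criterion 13, replace the reference to dosing with a stated period after the infusion that covers at least the 60-day study. The simplest choice is the wording already applied to men: during the study and for 3 months after administration. Carry the same period into the consent form and the eligibility checklist. As an editorial matter, move the sentence about men out of the list of methods for women and into its own numbered criterion.

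The cost is one phrase in an amendment, with matching consent and checklist lines. Under section 12.1 the amendment needs approval by the manufacturer, the IRB/IEC and, where required, the health authorities, and section 3 says each site holds its own IND. Sample size, visits and data collection do not change. A 3-month period would run about a month past the last scheduled contact (89 − 60 = 29 to 92 − 60 = 32 days), so the final weeks would rest on the woman's agreement, as they already do for men. A period ending with the study at Day 60 would avoid this and would still remove the conflict with sections 4.3 and 7.
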